## 11.5.9. Statistical Methods: Multiplicity

For the primary endpoint, a fixed sequence testing procedure will be used to control the Type I error rate. Statistical adjustment of p-values will not be performed.

# 12. INFORMED CONSENT, ETHICAL REVIEW, AND REGULATORY CONSIDERATIONS

### 12.1. Informed Consent

The Investigator is responsible for ensuring that the patient understands the potential risks and benefits of participating in the study, including answering any questions the patient may have throughout the study and sharing in a timely manner any new information that may be relevant to the patient's willingness to continue participation in the study.

The Informed Consent Form (ICF) will be used to explain the potential risks and benefits of study participation to the patient in simple terms before the patient is entered into the study, and to document that the patient is satisfied with his or her understanding of the risks and benefits of participating in the study and desires to participate in the study.

The Investigator is responsible for ensuring that informed consent is given by each patient or legal representative. This includes obtaining the appropriate signatures and dates on the ICF prior to the performance of any protocol procedures and prior to the administration of study drug.

## 12.2. Ethical Review

The Sponsor or its representatives must approve all ICFs before they are used at investigational sites(s). All ICFs must be compliant with the International Council on Harmonisation (ICH) guidelines on GCP.

Documentation of IRB/IEC/REB approval of the protocol and the ICF must be provided to the Sponsor before the study may begin at the investigational site(s). The IRB/IEC/REB(s) will review the protocol as required.

The study site's IRB/IEC/REB(s) should be provided with the following at a minimum:

- The current IB and updates during the course of the study
- ICF
- Relevant curricula vitae

## **12.3.** Regulatory Considerations

This study will be conducted in accordance with:

- 1. Consensus ethics principles derived from international ethics guidelines, including the Declaration of Helsinki and Council for International Organizations of Medical Sciences (CIOMS) International Ethical Guidelines
- 2. The ICH GCP Guideline [E6]
- 3. Applicable laws and regulations

The Investigator or designee will promptly submit the protocol to applicable IRB/IEC/REB(s). Some of the obligations of the Sponsor may be assigned to a third party organization (TPO).

An identification code assigned by the IXRS to each patient will be used in lieu of the patient's name to protect the patient's identity when reporting AEs and/or other study-related data.

## **12.3.1.** Investigator Information

Physicians with experience in metabolic bone disease will participate as investigators in this clinical study.

## 12.3.2. Protocol Signatures

The Sponsor's responsible medical officer will approve the protocol, confirming that, to the best of his or her knowledge, the protocol accurately describes the planned design and conduct of the study.

After reading the protocol, each Investigator will sign the protocol signature page and send a copy of the signed page to a Sponsor representative.

## 12.3.3. Final Clinical Study Report Signature

The Principal Investigator will sign the final clinical study report for this study, indicating agreement that, to the best of his or her knowledge, the report accurately describes the conduct and results of the study.

The Sponsor's responsible medical officer and statistician will approve the final clinical study report for this study, confirming that, to the best of his or her knowledge, the report accurately describes the conduct and results of the study.

## **12.4.** Publication Policy

The full terms regarding publication of the results of this study are outlined in the Clinical Study Agreement, Statement of Agreement, or the Master Clinical Study Agreement. Publication is permitted only after multi-center results are available and all disclosure requirements for clinical study registries have been met. Any data to be submitted for publication, including abstract submissions or presentations, are required to be submitted to Alexion for review at least 30 days prior to submission.

The process for identifying the coordinating Investigator will include evaluation of relevant criteria including, but not limited to: 1) enrollment of the greatest number of patients; 2) clinical experience with HPP; 3) demonstrated understanding of, and adherence to, this protocol; and 4) contribution to study development and/or implementation.

## 14. APPENDICES

## 14.1. Study AA-HPP-208: Clinical Laboratory Tests

## **Protocol AA-HPP-208: Clinical Laboratory Tests**

Hematologya:

Erythrocytes Hemoglobin Hematocrit

Red blood cell indices

Mean corpuscular volume reticulocytes Ret. mean corpuscular hemoglobin Ret. corpuscular hemoglobin content Reticulocyte distribution width White blood cell count and differential

Neutrophils, segmented

Lymphocytes Monocytes Eosinophils Basophils Platelets

Mean platelet volume

Urinalysisa:

pH
Protein
Glucose
Ketones
Bilirubin
Erythrocytes
Leukocyte esterase

Nitrite Urobilinogen Calcium

Calcium/Creatinine Microscopy

Abbreviations: ret. = reticulocyte

a Assayed by Alexion-designated laboratory

b Results will be confirmed at Screening

c Local or Investigator-designated laboratory

Clinical Chemistrya:

Sodium Potassium Total bilirubin Direct bilirubin Indirect bilirubin Alkaline phosphatase

Alanine aminotransferase (ALT) Aspartate aminotransferase (AST) Blood urea nitrogen (BUN)

Blood urea nitrogen (BUN)
Creatinine
Urea

Phosphate Glucose, fasting Albumin

Calcium

Protein Carbon dioxide Magnesium Chloride

Other Laboratory Testsa
Parathyroid hormone, intact

25-OH Vitamin D

**Pregnancy Test** (female patients only)b,c

Choriogonadotropin Beta

#### 14.2. Study AA-HPP-208: Sampling Summary

This table summarizes the approximate number of samples and volumes for all sampling and tests during the study. Fewer samples may actually be taken, but this will not require a protocol amendment.

Protocol AA-HPP-208: Sampling Summary per Patient

Purpose	Sample Type	Approximate Amount per Sample	Approximate Number Samples	Approximate Total Amount
Screening tests a	Blood	2.5 mL	6	15.0 mL
Standard laboratory tests a	Blood	2.5 mL	20	50.0 mL
Pharmacokinetic samples	Blood	2.5 mL	46	115.0 mL
Pharmacodynamic samples.b	Blood	2.0 mL	96	192.0 mL
Immunogenicity samples	Blood	2.5 mL	12	30.0 mL
Total	Blood	12.0 mL	182	402.0 mL

a Additional samples may be drawn if needed for safety purposes.
b Plasma inorganic pyrophosphate (PPi) and plasma pyridoxal-5' phosphate (PLP)

16 December 2015

## RE: Administrative Change Letter: Protocol Clarifications

Protocol AA-HPP-208: A Phase 2a, Randomized, Multicenter, Open-Label, Pharmacokinetic, and Dose Response Study of Asfotase Alfa in Adult Patients with Pediatric-Onset Hypophosphatasia

To whom it may concern:

This letter is to clarify the following:

- Dose adjustment: The process for dose adjustment is inconsistent in Section 8.1 and Section 8.5 of the protocol. This letter is to clarify that total amount of asfotase alfa will be adjusted once a week at study visits (in-clinic or home) to account for body weight change. The number of vials used to prepare injections will be determined based on the patient's weight at that visit. The same number of vials and total amount of asfotase alfa will be administered until a new weight is recorded.
- **Electronic Diary:** Study drug administration data will be entered into an electronic diary by the home health care nurse or site staff. The protocol has inconsistent description of the process in Sections 8.5, 8.8, and 10.1 and Table 2, footnote 21. Full instructions for data collection using an electronic diary will be provided in the Study Operations Manual.
- Pregnancy Testing: Pregnancy testing will be performed during in-clinic visits (Screening, Run-in, Week 1, Week 9, and Week 13). In the protocol, the timing of pregnancy testing is described inconsistently in Section 6.2 and Table 2, footnote 13. This clarification will also be included in the Study Operations Manual.
- Drug Accountability: Patients will be instructed to return any used study drug at the next study visit for the purpose of performing drug accountability. This process is described inconsistently in Section 8.8 and will be further clarified in the Pharmacy Manual.
- Reporting of Serious Adverse Event (SAE): In Section 9.4.1.11, the protocol lists Patient's Registry ID number as one of the required information for SAE reporting. However, there is no Registry ID number in this study. The information expected is the Patient's ID number.
- Clinical Laboratory Tests: Red blood cell indices (which include Mean corpuscular volume reticulocytes, Ret. mean corpuscular hemoglobin, Ret. corpuscular hemoglobin content, Reticulocyte distribution width) and mean platelet volume are listed in the Appendix 14.1; however, these labs were included inadvertently and will not be implemented for this study. Erythrocytes assay is listed under Hematology; however, the intended assay is Red Blood Cell Count and will be clarified in the Laboratory Manual. Additionally, Blood urea nitrogen (BUN) and Urea are listed under Clinical Chemistry; however, the

intended test is Urea nitrogen and will be further clarified in the Laboratory Manual.

- **Nomenclature for Pre-dose Sampling:** The pretreatment/Baseline sampling (prior to the first dose of asfotase alfa) will occur at -168h, -156h, -24h, and immediately prior to the first dose (pre-dose). In Table 2 (first bulleted footnote), Table 3 (first bulleted footnote), and Section 11.5.1, this 'pre-dose' sample is designated as '0h' (Hour 0); however, in all places this sampling time is referred to as 'pre-dose.'
- Schedule of Events: Further information on the timing and schedule of assessments will be included in the Study Operations Manual.
- **Fasting Criteria**: Footnote 15 in Table 2 clarifies the protocol requirements for fasting. This requirement as stated in Table 2, footnote 15 also applies to Table 3.

Sincaraly PPD		
PPD		

Cc: eTMF, ISF

PPD Project Manager

Alexion Pharmaceuticals, Inc.

**Protocol AA-HPP-208:** A Phase 2a, Randomized, Multicenter, Open-Label, Pharmacokinetic, and Dose Response Study of Asfotase Alfa in Adult Patients with Pediatric-Onset Hypophosphatasia

Date: 01 April 2016

Administrative Change Letter #2

To: PPD

There have been changes associated with the Study AA-HPP-208 protocol, dated 16 November 2015. Effective immediately, the following changes are in effect:

- The estimated date for first patient enrolled in Study AA-HPP-208 has been extended to Q2 2016.
- The estimated date for first patient completed in Study AA-HPP-208 has been extended to Q3 2016.
- Study drug administration data will be entered into an electronic diary by the home health care nurse or site staff. The protocol has inconsistent description of the process in Sections 7.2, 8.5, 8.8, and 10.1 and Table 2, footnote 21. Full instructions for data collection using an electronic diary will be provided in the Study Operations Manual.
- Screening serum creatinine or parathyroid hormone (PTH) levels ≥1.5 times the upper limit of normal is an exclusion criterion.
- All prior and concomitant medications and therapies must be collected from 30 days prior to study entry up until the final study visit. The protocol has inconsistent description of the process for the collection of Concomitant medications and therapies in Table 2, footnote 9 and Section 8.7.
- All pre-dose PK/PD/ADA samples during the Run-in Period and Main Study Period (Treatment Period) must be collected under fasting conditions, except for Day -7, -156 hour and Day -1, -12 hour samples. The post-dose PK/PD/ADA samples will not be collected under fasting conditions.
- Effective March 3rd, 2016, the Drug Safety Physician of this protocol is

Title: PPD Email: PPD

Phone number: PPD

If there are any questions concerning this change, please contact PPD by phone at PPD or by email at PPD This change will be captured in the next protocol amendment.

Sincerely.	PPD	
PPD		

Alexion Pharmaceuticals, Inc. [name]

Cc: eTMF, ISF
PPD Project Manager

# 3. LIST OF ABBREVIATIONS AND DEFINITIONS OF TERMS

The following abbreviations and acronyms are used in this SAP.

Table 1:Abbreviations and acronyms

Abbreviation or acronym	Explanation				
ADA	Anti-drug antibodies				
AE	Adverse event				
AESI	Adverse events of special interest				
ALP	alkaline phosphatase				
ANCOVA	analysis of covariance				
ATC	anatomic class				
CI	Confidence Interval				
CS	Clinically significant				
FA	Full Analysis				
HPP	Hypophosphatasia				
IAR	Injection associated reaction				
ISR	Injection site reaction				
kg	kilogram				
LOCF	Last Observation Carried Forward				
MedDRA	Medical Dictionary for Regulatory Activities				
mg	milligram				
mL	milliliter				
mmHg	millimeters of mercury				
NAb	Neutralizing antibodies				
OC	Observed Case				
PD	Pharmacodynamic				
РК	Pharmacokinetic				
РР	Per Protocol				
PLP	pyridoxal 5'-phosphate				
PPi	inorganic pyrophosphate				
РТ	Preferred Term (MedDRA)				
PTAEs	Pre-Treatment Adverse Events				
PTH	Parathyroid Hormone				
REML	restricted maximum likelihood				
SAE	Serious adverse event				
SAP	Statistical Analysis Plan				
$SAS^{ embed{matrix}}$	Statistical Analysis Software ®				
SD	standard deviation				
SOC	System Organ Class (MedDRA)				
TEAEs	Treatment-Emergent Adverse Events				
TNSALP	tissue-nonspecific alkaline phosphatase				

# 4. **DESCRIPTION OF THE PROTOCOL**

The AA-HPP-208 study, "A Phase 2a, Randomized, Multicenter, Open-Label, Pharmacokinetic, and Dose Response Study of Asfotase Alfa in Adult Patients with Pediatric-Onset Hypophosphatasia" is a post-authorization commitment for European Medicines Agency(EMA) to evaluate the pharmacokinetics (PK) and pharmacodynamics (PD) of asfotase alfa following administration of a range of dose regimens that encompasses the dose proven to be effective in children (6.0 milligram [mg]/kilogram[kg]/week) in adult patients with pediatric-onset hypophosphatasia (HPP). A secondary objective is to evaluate the safety and tolerability of asfotase alfa in adult patients with pediatric-onset HPP. The protocol can be referenced for additional details. The schedule of events is attached in Appendix 9.1 of this statistical analysis plan (SAP).

# 4.1. Changes from Analyses Specified in the Protocol

The primary analysis of the primary endpoint, the change in PPi from Baseline to pre-3rd dose Week 9 has been changed from non-parametric exact Wilcoxon rank-sum test into a restricted maximum likelihood (REML)-based repeated measures mixed model; while non-parametric exact Wilcoxon rank-sum test becomes a supportive analysis.

The Per Protocol Set criteria for study drug compliance has been modified as 100% compliance (i.e. all doses of study drug) is too restrictive. A slightly revised definition will be utilized requiring that patients receive 100% of study drug as planned on Weeks 8 and 9, and at least 80% of study drug overall as specified in the protocol.

All prior and concomitant medications and therapies must be collected from 30 days prior to study entry up until the final study visit. The protocol has inconsistent description of the process for the collection of Concomitant medications and therapies in Table 2, footnote 9 and Section 8.7; this is being clarified with an administrative letter.

# 4.2. Changes from Analyses Specified in the Previous Version of the Statistical Analysis Plan

This document describes the SAP for final data analyses for the study. The following additions since the previous version 1.0 of the final SAP will apply:

- The primary analysis of the primary endpoint has been changed, as described in Section 4.1. Analysis of covariance (ANCOVA) will be added as sensitivity analyses. A repeated measures mixed model with fixed, categorical effect of visit will be replaced by the same model with the fixed, categorical effect of visit, adjusted for baseline PPi.
- Sensitivity analyses may be employed to exclude biologically implausible outliers in PPi and PLP.
- The following Adverse Events of Special Interest (AESI) will be added for consistency across the asfotase afa development program:
  - Ectopic calcification

- Lipodystrophy
- Craniosynostosis
- Chronic hepatitis
- Analyses on anti-drug antibody (ADA) status and neutralizing antibody (NAb) status at Baseline and post-Baseline will be added. Time to first ADA positive, ADA positive continuously, ADA peak titer, ADA high titer category (>128) and NAb positive will also be summarized.

# 5. **DEFINITIONS**

#### 5.1. Efficacy/Pharmacodynamics

#### 5.1.1. Primary Endpoint

The change in inorganic pyrophosphate (PPi) from Baseline to pre-3rd dose Week 9. Baseline is defined as the average of all available pre-dose PPi assessments prior to first SC injection with asfotase alfa (-168, -156, -24, -12h, and pre-dose Day 1). Pre-3rd dose Week 9 is defined as the value obtained prior to the 3rd dose during Week 9.

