(3 times per	Week 4	Day 22: pre-dose, post-dose 6h	D22, D24, D26	All	Day 22: pre-dose
week)	Week 5	Day 29: pre-dose (trough), post-dose 6h	D29, D31, D33	All	Day 29: pre-dose
	Week 6	None	D36, D38, D40	None	None
	Week 7	Day 43: pre-dose (trough), post-dose 6h	D43, D45, D47	All	Day 43: pre-dose
	Week 8	Day 50: pre-dose (trough), post-dose 6h	D50, D52, D54	All	Day 50: pre-dose
	Week 9	Day 57: pre-dose Day 61: pre-dose (trough), post-dose 6h, 12h Day 62:post-D61 dose 24h, 32h, 36h, Day 63:post-D61 dose 48h, 56h, 60h	D57, D59, D61	All	Day 61: pre-dose
No Dosing	Week 10	Day 64: post-D61 dose 72h Day 65: post-D61 dose 96h Day 66: post-D61 dose 120h Day 67: post-D61 dose 144h Day 68: post-D61 dose 168h	None	All	Day 68: post-D61 dose 168h
	Week 11	Day 71: post-D61 dose 240h Day 75: post-D61 dose 336h	None	All	Day 75: post-D61 dose 336h
	Week 12	Day 80: post-D61 dose 456h	None	All	Day 80: post-D61 dose 456h
	Week 13	Day 87: post-D61 dose 624h	None	All	Day 87: post-D61 dose 624h

Abbreviations: ADA = anti-drug antibodies; PK = pharmacokinetics; PLP = pyridoxal 5'-phosphate; PPi = inorganic pyrophosphate; SOM = Study Operations Manual; D = day; h = hour

NOTE: Trough is defined as pre-dose concentration (ie, concentration data-point collected just prior to the next dose).

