#### 7.2.1.1. Handling of Dropouts or Missing Data

The protocol schedule requires 5 pre-treatment baseline PPi samples (-168, -156, -24, -12h, and pre-dose Day 1) be collected. The average value will be used for calculating Baseline PPi; therefore, at least 1 pretreatment baseline observation is required for the patient to be included for the assessment of the primary analysis. Patients will also be required to have at least 1 on-treatment PPi observation to be included in the FA Set. For the analyses of changes from Baseline using repeated measures mixed modeling, missing values will not be imputed based on a Missing at Random Assumption (MAR). Missing values at the pre-3rd dose Week 9 assessment will be imputed with the last available on-treatment pre-dose trough assessment prior to pre-3rd dose Week 9 using LOCF. This imputation will occur where indicated.

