#### 7.2.2. Secondary Endpoint

For the secondary endpoint, PLP change from Baseline to pre-3rd dose Week 9, similar methods as for PPi will be employed in the FA Set and PP Set.

Sensitivity analyses for PLP may be employed for any patients without taking any vitamin B6 or with consistent input of vitamin B6, defined as taking same dose of vitamin B6 during the study. Vitamin B6 usage will be obtained from the concomitant medications.

Additionally for sensitivity, the within-patient mean absolute levels of the pre-treatment "fasting" PLP samples (-168 h, -24 h, pre-dose Day 1) and the "non-fasting" PLP samples (-156 h, -12 h) will be compared using the exact Wilcoxon rank-sum test for all patients in the FA Set. If a statistical difference is detected between the pre-treatment "fasting" and "non-fasting" samples, given samples on treatment are collected under both "fasting" and "non-fasting"

conditions, the change to each post-treatment timepoint will be evaluated descriptively using the matched "fasting" or "non-fasting" average at Baseline; accordingly, "fasting" post-treatment samples will use a "fasting" Baseline and "non-fasting" post-treatment samples will use a "non-fasting" Baseline.

Please refer to Table 4 on how to handle the values fall under the lower limit of quantification (LLOQ).

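### Baseline PPi mixes three fasting and two non-fasting samples while the Week 9 endpoint is fasting; the plan checks this for PLP only, so within-cohort PPi changes could be shifted, though the primary between-cohort contrast is not biased in expectation

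*SAP*

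**What the plan says.** **Baseline.** SAP 5.1.1 says "Baseline is defined as the average of all available pre-dose PPi assessments prior to first SC injection with asfotase alfa" and lists -168 h, -156 h, -24 h, -12 h and Day 1 pre-dose. SAP 7.2.1.1 adds: "The average value will be used for calculating Baseline PPi; therefore, at least 1 pretreatment baseline observation is required". One sample is therefore enough.

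**Fasting status.** Administrative Change Letter #2 says that pre-dose PK, PD and antibody samples "must be collected under fasting conditions, except for Day -7, -156 hour and Day -1, -12 hour samples". It adds that post-dose samples are not taken fasting.

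**Endpoint.** The primary endpoint uses the single value before the third dose of Week 9. Protocol Table 3 lists it as "Day 61: pre-dose (trough), post-dose 6h, 12h", and the letter makes the pre-dose sample a fasting one. The same holds for every pre-dose timepoint in the primary model (SAP 7.2.1, Day 22 to Day 61).

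**Existing safeguard.** SAP 7.2.2 labels the same samples fasting and non-fasting for PLP and compares the two within-patient means with an exact Wilcoxon rank-sum test. If that test is significant, "the change to each post-treatment timepoint will be evaluated descriptively using the matched" fasting or non-fasting baseline. SAP 7.2.1 and 7.2.1.5 contain nothing equivalent for PPi. The statement in 7.2.2 that PLP follows PPi methods carries methods from PPi to PLP, not the reverse.

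**The concern.** A change from Baseline is easiest to interpret when both ends are measured under the same conditions. Here two-fifths of the baseline comes from samples that differ from the endpoint sample in fasting requirement and in time of day. The plan recognises the issue for the secondary endpoint but is silent for the primary one.

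At stake are planned outputs that describe each cohort on its own: the model-estimated mean change at each visit with its 95% CI and p-value (SAP 7.2.1), and the signed-rank tests within cohort. The primary objective is to describe PK and PD across dose regimens, so these estimates will be read in their own right. Any food or time-of-day effect on PPi would be counted in them as drug effect.

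The PLP safeguard also has two weaknesses. A rank-sum test treats two means from the same patients as independent groups. And the matched baseline appears only after a significant result, although a non-significant test in about 27 patients does not show that the difference is negligible.

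**Working it through.** **Plan's own power figures.** Two-sample t-test, 2-sided 0.05, SD 1.5 µM, per comparison (noncentral t):
- 9 per cohort, difference 2.3 µM: 86.3% (plan: more than 80%)
- 6 per cohort, difference 3.2 µM: 91.4% (plan: more than 90%)

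Both reproduce.

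**Offset within a cohort.** Let F be a patient's fasting PPi before treatment and d the non-fasting minus fasting difference, which here includes any time-of-day effect.

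Baseline = (3F + 2(F + d)) / 5 = F + 0.4d

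Fasting pre-dose change = true change - 0.4d

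| Assumed size of d (µM) | Size of shift (µM) |
|---|---|
| 0.25 | 0.10 |
| 0.5 | 0.20 |
| 1.0 | 0.40 |

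The sign follows the sign of d, which is unknown. Administrative Change Letter #1 omits -12 h from its list of run-in samples. With four samples the weight would be 1/4 and the shift 0.06 to 0.25 µM. Letter #2 and the SAP keep -12 h, so 3 + 2 is the operative reading.

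**Within-cohort signed-rank test.** Simulated with n = 9, SD 1.5 µM and no drug effect, the rejection rate is about 4% at d = 0, 5% at |d| = 0.5 µM and 9% at |d| = 1.0 µM. The test is discrete: its exact null level at n = 9 is 20/512 = 3.9%.

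**Between-cohort contrast, common d.** Each cohort shifts by -0.4d, so the difference is -0.4d - (-0.4d) = 0. Adjusting for baseline PPi does not alter this, because adding a constant to everyone's baseline leaves the slope and the cohort difference unchanged. Simulated type I error of the t-test was 4.9% to 5.3%.

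**Between-cohort contrast, d varying between patients with SD τ.** The variance of the change rises by 0.4² × τ² = 0.16τ². This treats 1.5 µM as excluding that variation and ignores baseline adjustment.

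| τ (µM, assumed) | SD of change (µM) | Power, 9 per cohort, 2.3 µM | Power, 6 per cohort, 3.2 µM |
|---|---|---|---|
| 0 | 1.50 | 86.3% | 91.4% |
| 0.5 | 1.51 | 85.7% | 90.9% |
| 1.0 | 1.55 | 83.9% | 89.5% |
| 1.5 | 1.62 | 80.9% | 87.0% |

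**Between-cohort contrast, unequal sample mix.** If one-third of one cohort lacked both non-fasting samples, the contrast would move by (1/3) × 0.4 × d: 0.07 µM at d = 0.5 and 0.13 µM at d = 1.0.

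**The case against.** The strongest reply is that the primary hypotheses compare randomised cohorts with the same planned sampling and adjust for baseline PPi. A common offset then cancels. That stands. A reader might infer from the mixed baseline that the primary test is biased, or might express the 0.1 to 0.4 µM shift as a share of the 2.3 µM planning difference. Neither follows: the shift belongs to a cohort's own change, whereas 2.3 µM is a difference between cohorts, in which the shift is zero in expectation.

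Nothing in the documents says that PPi depends on food or time of day. The PLP check sits beside a vitamin B6 analysis, so it may reflect a dietary concern specific to PLP. The missing PPi counterpart therefore cannot be called an oversight, and even the existence of a non-zero d is an assumption. Nor does Letter #2 say that patients have eaten before the exempt samples. But the documents do not state that PPi is insensitive either, and the data to find out are already collected.

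Under the one-sample rule, the non-fasting share could in principle run from 0% to 100% for a patient. The run-in and Day 1 samples fall at required in-clinic visits, so the extremes are unlikely.

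A reader might also want every post-dose change matched to the -156 h/-12 h mean. Samples at 24, 48, 72 h and later fall at the dosing clock time, so that would trade a fasting mismatch for a clock-time mismatch.

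Finally, absolute PPi levels are also summarised and plotted, and the baseline definition does not affect those.

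**Conclusion.** The sampling mismatch is documented, and the plan has no safeguard for PPi. Its reach is limited to each cohort's estimated pre-dose change, the accompanying intervals and p-values, and the within-cohort signed-rank tests. All are shifted by -0.4d, or 0.1 to 0.4 µM in size for an assumed |d| of 0.25 to 1.0 µM of either sign.

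The primary between-cohort comparison remains valid in expectation. It is affected only by a modest loss of precision if d varies between patients, or by a small shift if the available samples differ by cohort. The documents do not support a claim that the primary result is wrong. This is a low-cost improvement to the interpretation of the PD results. It rests on two assumptions: that d is not zero, and that it acts additively.

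**What to change.** Keep the five-sample baseline as primary. Add to SAP 7.2.1.5:

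1. A prespecified sensitivity run of the primary model and the within-cohort tests at the fasting pre-dose timepoints (Days 22 to 61), with Baseline taken as the mean of the available fasting samples only (-168 h, -24 h, Day 1 pre-dose). Do this for PPi and PLP, whatever the result of any significance test, and report it beside the five-sample version.
2. The within-patient fasting versus non-fasting baseline difference for PPi and PLP, with a paired (signed-rank) analysis in place of the rank-sum test in SAP 7.2.2.

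Do not extend the non-fasting baseline to all post-dose samples.

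**Cost.** SAP wording and one further set of model runs; no new samples. A three-sample mean has a within-patient standard error √(5/3) = 1.29 times that of a five-sample mean, about 29% larger if samples are independent. That is the reason to report both versions and not to replace the primary baseline.
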